**Table 2 – Validated Survey Instrument Descriptions\***

Validated Survey Instrument	Description
System Usability Survey (SUS)	SUS is a computer self-efficacy measures questionnaire that has long been used to assess a user’s belief that they have the capability to successfully interact with a computer system. Based on social psychology, self-efficacy has been found to influence the user’s behavior related to use of the system  . Within the domain of healthcare, patients must see themselves as capable of successfully using the PHR  . The ten question survey asks the patient to indicate whether they are able to complete a task under a variety of conditions, such as step by step instructions, on-call user help, or initial training in getting started  .
Medication Adherence Survey (MAS)	The MAS is an eight question patient survey that provides reliable predictions of patient medication compliance  . The MAS has a strong correlation with clinical outcomes in patients with hypertension and other conditions  . Patients with greater knowledge, attitude, satisfaction and coping skills were more likely to have high medication adherence, those stressed or requiring a complex medication scheme were less likely to be adherent  .
Patient Activation Measure (PAM)	The patient activation measure (PAM) is a 13 question survey using a 4-point Likert scale. It is a robust and well-validated assessment tool developed by Hibbard and colleagues  to measure the level of patient engagement in their health. The PAM is a scale that reflects a developmental model of activation. Activation appears to involve four stages: (1) believing the patient role is important, (2) having the confidence and knowledge necessary to take action, (3) actually taking action to maintain and improve one’s health, and (4) staying the course even under stress. PAM scores are independent of traditional socio-economic and demographic such as race, income or education and instead emphasize what the patient can do to help themselves. Hibbard et al. demonstrated that coaching improves PAM scores, medication adherence and reduces re-hospitalization rates  .
Atrial Fibrillation Knowledge Scale	The AF Knowledge Scale is a validated tool that consists of 11 items concerning AF in general, symptom recognition. This tool was developed due to a need for a specific instrument to detect gaps in the knowledge of AF patients. The AF Knowledge Scale can be successfully used in an outpatient care setting as an important tool in the tailoring of patient education  .
Newest Vital Sign (NVS)	The NVS is a validated instrument that screens for health literacy in approximately three minutes  . Participants are given a nutrition label, and then asked six questions about it. A score of 0-1 suggests a high likelihood of limited literacy; a score of 2-3 indicates the possibility of limited literacy; a score of 4-6 indicates adequate literacy  . The NVS has been found to provide results comparable to more extensive health literacy tests  , but it is considered to be the most practical tool because it also assesses numeracy, an element of health literacy that is often not represented in other tools  .

Altarum Consumer Engagement (ACE) Measure	The Altarum Consumer Engagement (ACE) measure is a 12 question survey validated to assess a patient’s level of engagement in their health using the three domains of commitment, informed choice, and navigation. The ACE measure expands upon other validated survey instruments and broadens the measurement of engagement by including questions related to modern sources of information, such as online health resources and provider ratings. The survey serves as a reliable predictor of health status, health behaviors, medication adherence, and health resource utilization  .
Ten-Item Personality Inventory (TIPI)	The Ten-Item Personality Inventory (TIPI) measure is a 10-item measure of the Five-Factor Model. The psychometrics for the TIPI are known and reasonable. This measure provides for an assessment to be completed in less than one minute, far less than other personality measures.

\* The items from each of these survey instruments, along with demographics, will be incorporated into participant surveys to be administered during the focus groups and technology trial.

**b.) Design Survey**

The secure online program, Survey Monkey will be used to administer the survey. After prospective participants have been identified, and it is confirmed that they meet the inclusion criteria, the research team will contact individuals to participate in the survey. Potential participants will be contacted through up to three methods as applicable per patient: MyChart message, email, or letter. If individuals wish to participate, they will be instructed through MyChart, email, or letter to access the informed consent and subsequent survey through the provided secure link to Survey Monkey. Individuals who have read and agree to the informed consent online, will then be able to access the online survey. Subjects may opt out of taking the survey at any time. Recruitment and survey materials are additionally being submitted for IRB review.

Survey Monkey enables covered entities to collect protected health information (PHI) in online surveys in a way that permits compliance with the Health Insurance Portability and Accountability Act of 1996 (HIPAA). SSL (Secure Sockets Layer), a protocol developed for transmitted private documents or information via the internet, creates a secure connection between a client and a server, encrypting sensitive information being transmitted through the web page. SSL encryption is automatically turned on for all Survey Monkey surveys in this study. IP (Internet Protocol) address may be tracked to prevent the survey from being taken twice, but this information will not be collected by the research team. However, we will collect participant name and email address in order to send their eGiftcard compensation.

The surveys will be received by research staff and analyzed. The information will be used to develop content for an intervention aimed at enhancing medication adherence.

***i. Patient Selection***

a) Study Population: The study population for the survey is comprised of all adult, ambulatory PPG-Cardiology patients with non-valvular atrial fibrillation who are taking an oral anti-coagulant medication.

b) Sample Size:  $5 \leq N \leq 150$

c) Inclusion/Exclusion Criteria:

Inclusion Criteria

1. Diagnosis of Atrial Fibrillation (Paroxysmal, Persistent, Permanent)
2. Receiving Oral Anticoagulation (VKA or NOAC) for non-valvular AF
3. Physically and Mentally capable of providing Informed Consent
4. Age 18 years or older
5. Ability to read and understand English
6. Current Patient of PPG-Cardiology

Exclusion Criteria

1. Absence of History of Atrial Fibrillation (AF)
2. Does not meet Inclusion Criteria
3. Anticoagulation with VKA or NOAC for reasons other than non-valvular AF

d) Enrollment:

A list of adult patients who meet inclusion criteria will be provided by the Anticoagulation Therapy Unit (ATU) Clinic and Parkview Physicians Group-Cardiology. If needed, an additional list of adult patients who meet inclusion criteria will be obtained from patient records at Parkview Physicians Group-Cardiology using Epic reporting tools. Research staff will review these patient charts to identify if they meet inclusion criteria, or if factors in the exclusion criteria are identified. This study will not affect patient standard of care. Before contacting patients, approval will be obtained in Epic from each patient's primary cardiologist, as well as the principal investigator. Focus Group patients who indicated they would like to be contacted for future phases of the study will also be contacted.

Research staff will contact patients by MyChart message, email, or letter. Patients will be sent up to two reminders to participate in the survey if they wish. Patients who are interested in participation will be able to access the survey through the secure link provided in the MyChart message, email, or letter. Patients will be presented to informed consent in Survey Monkey immediately preceding the survey questions.

## ***ii. Survey Questions***

A copy of the survey questions, as they will appear in Survey Monkey, is included in the submission packet for IRB review.

## **c.) Wireframe Prototyping and Testing (Design Session)**

During the study design sessions, we will use value-based software engineering and agile development methods to link the diverse group of patients with experts in human-computer interaction (HCI) to create models of desired PHR workflow.

### ***i. Patient Selection***

- a) Study Population: The study population for the individual design sessions is comprised of all adult, ambulatory PPG-Cardiology patients with non-valvular atrial fibrillation who are taking an oral anti-coagulant medication.
- b) Sample Size:  $5 \leq N \leq 20$
- c) Inclusion/Exclusion Criteria:

#### Inclusion Criteria

1. Diagnosis of Atrial Fibrillation (Paroxysmal, Persistent, Permanent)
2. Receiving Oral Anticoagulation (VKA or NOAC) for non-valvular AF
3. Physically and Mentally capable of providing Informed Consent
4. Age 18 years or older
5. Ability to read and understand English
6. Current Patient of PPG-Cardiology

#### Exclusion Criteria

1. Absence of History of Atrial Fibrillation (AF)
2. Does not meet Inclusion Criteria

3. Anticoagulation with VKA or NOAC for reasons other than non-valvular AF

d) Enrollment:

A list of adult patients who meet inclusion criteria will be provided by the Anticoagulation Therapy Unit (ATU) Clinic and Parkview Physicians Group-Cardiology. If needed, an additional list of adult patients who meet inclusion criteria will be obtained from patient records at Parkview Physicians Group-Cardiology using Epic reporting tools. Research staff will review these patient charts to identify if they meet inclusion criteria, or if factors in the exclusion criteria are identified. This study will not affect patient standard of care. Before contacting patients, approval will be obtained in Epic from each patient's primary cardiologist, as well as the principal investigator. Patients who participated in the focus groups and/or the survey who indicated they would like to be contacted for future phases of the study will also be contacted. Research staff will contact patients by telephone. Patients who are interested in participation will be mailed a copy of the informed consent to review prior to their scheduled individual design session. Each patient will undergo the informed consent process immediately preceding their designated design session.

**ii. Study Design**

We will incorporate the use of modeling tools called “wireframes” as part of our user interface design process to generate a prototype. Wireframes are said to be a best practice when designing user interfaces and are especially helpful for interactive projects that are complex and require quick iterative changes. It allows users to see changes instantly. Using the wireframe modeling tool we can start with gray box wireframes and evolve them from low-fidelity to high-fidelity user interface design with ease. Low-fidelity modeling may be as simple as a rough sketch. The creation of PHR models using wireframes will allow us to alter the user interface, often in a matter of minutes so that users can see their suggestions immediately.

Many wireframe tools allow the incorporation of interactivity including flash animation, and front-end web technologies such as, HTML, CSS, and JavaScript. Other features of wireframe tools include: the ability for the

designer to easily drag and drop components, a presentation mode to test wireframe interactions, a revision history for tracking design iterations, access to large libraries of wireframe components, real-time collaboration with all team members through a chat option, and access to a whiteboard for drawing doodles on wireframes.

These “wireframes” help a project team collaborate more effectively since they are more abstract, using rectangles and labeling to represent content. High-fidelity “wireframes” can easily be passed along to developers for implementation because they incorporate a level of detail that matches the design of the fully functional user interface.

The wireframes, after being produced by the research staff, will be evaluated through one-on-one design sessions. This session involves priming a participant with a fictitious scenario and observing their interaction with the system to find relevant content. The objective of this exercise is to identify how successfully the proposed design meets their education and information requirements. In addition, each design session will involve completion of the survey administered in the previous phase (Design Survey) and participation in closing discussion questions. Patients who previously participated in the design survey will not need to retake the survey. The survey, closing discussion questions, and scenarios for patient use are included in the submission packet for IRB review.

Each of these individual sessions will last one to two hours and will be video recorded, with participant permission. Qualitative data from the recorded interviews may be used to iteratively adjust the wireframe models with each design session. The final wireframes will help the project team validate the planned design.

#### **d.) Intervention Build**

We will apply what we learned in the iterative design process described in parts a) and b) above to build a working prototype in a PHR, Epic’s MyChart. One trigger for health education messaging used in the intervention will be failure to take, fill, or refill anticoagulant medication prescription – information obtained from an e-prescribing data feed to the electronic medical record (Surescripts) and use of the AdhereTech smart pill bottle (HIPAA compliant, FDA-registered Class I medical device) that sends notification in real time when participants open or fail to open their pill bottle. Thus, we will build in the necessary elements in the technology to create triggers for push messaging of health information through

[figure not shown]
the PHR. We will perform robust testing of the intervention and make adjustments as needed.

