Purpose	
This study is designed to develop patient focused strategies that improve adherence to anticoagulant medication in patients with non-valvular atrial fibrillation (AF). There are two phases to the study: Intervention Development and Intervention Trial. The intervention to be developed during Phase 1 includes tailored health education messaging delivered through a personal health record, MyChart. During the development of the intervention in Phase 1 we will use a patient-centered, iterative design process that includes interviews, prototype development and testing. One trigger for health education messaging will be failure to take, fill, or refill anticoagulant medication prescription – information obtained from an e-prescribing data feed to the electronic medical record (Surescripts) and use of a smart pill bottle (AdhereTech – HIPAA compliant, FDA-registered Class I medical device) that sends notification in real time when participants open or fail to open their pill bottle. The intervention trial in Phase 2 will be comprised of two groups, control and experimental. Both the control and experimental group will receive standard care, which includes access to MyChart. In addition to standard care, both groups will receive training on the use of MyChart and the AdhereTech smart pill bottle, and medication adherence for both groups will be monitored with Surescripts e-prescribing software and AdhereTech smart pill bottle use. The experimental group will receive the intervention: tailored health messaging delivered via MyChart pertinent to AF and oral anticoagulant use. Outcomes of this work include a novel intervention, as well as information regarding patient preferences for tailored education.
 
Specific Aims: Aim 1: Determine AF patient preference for content, timing, and delivery mode of tailored educational information about AF and anticoagulant therapy; Aim 2: Determine the impact of tailored messaging via personal health record on adherence to anti-thrombotic therapy and health outcomes in people living with AF; Aim 3: Determine the feasibility of measuring medication adherence with queries to electronic prescribing software and use of ‘smart’ pill bottles.

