**Table 1 – High-level timeline for 24-month study**

	Specific Aims	Methods	Timeline*
Phase 1 – Intervention Design and Build	Aim 1: Determine AF patient preference for content, timing, and delivery mode of tailored educational information about AF and anticoagulant therapy	Intervention design: focus groups; wireframe modeling of interaction	~0-6 months
		Intervention build: build trigger from Surescripts data feed and AdhereTech smart pill bottle; implement educational messaging in PHR	~3-10 months
Phase 2 – Intervention Trial	Aim 2: Determine the impact of tailored messaging via personal health record on adherence to anti-thrombotic therapy and health outcomes in people living with AF.	2-arm, 6-month trial of PHR intervention (N= ~160)	~10-22 months
	Aim 3: Determine the feasibility of measuring medication adherence with queries to electronic prescribing software and use of 'smart' pill bottles		
Dissemination	Data analysis and manuscript preparation	Target both cardiology and health informatics venues	~22-24 months

\*Timeline is based on approximate (~) dates

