## 2.) PHASE 2: INTERVENTION TRIAL

*Aim 2: Determine the impact of tailored messaging via personal health record on adherence to anti-thrombotic therapy and health outcomes in people living with AF.*

*Aim 3: Determine the feasibility of measuring medication adherence with queries to electronic prescribing software and use of ‘smart’ pill bottles.*

During the last 12 months of our study, we will conduct a 6-month trial of the intervention designed and built in Phase 1 of the study to examine the impact on patient engagement and medication adherence. Patients who meet inclusion criteria and agree to participate will be randomly assigned to one of two groups – Experimental or Control. The research team will alternate random assignment to experimental or control group in order to achieve equal numbers of patients receiving VKA and NOAC medication across both groups. Please see Figure 2 below, outlining the study group assignment process.

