#### **Separate from standard of care:**

- Receive an AdhereTech smart pill bottle to use for dispensing their anticoagulation medication at home.
- Receive training on the use of the AdhereTech smart pill bottle and commit to using in their daily routine for their anticoagulant medication
- Receive one-on-one training aimed at use of the MyChart PHR
- Use the PHR intervention: patients in this group will have the MyChart intervention designed and built in Phase 1 of this study – tailored health messaging delivered via MyChart pertinent to non-valvular atrial fibrillation and oral anticoagulation and stroke.
  - In addition to the tailored health messaging, patients will also receive periodic messages asking them to evaluate the health information they have received.
- Participate in an initial study visit, which includes the enrollment and training process above, as well as one follow up study visit and exit interview at approximately 6 months.
- Complete a patient survey at the initial study visit and follow up visit at approximately 6 months
- Submit information about their prescription history related to their anticoagulant medication for the study period
  - Patients may obtain this information from their pharmacy or print it out from their online pharmacy account. Patients will receive a letter from the Principal Investigators and a Medication dispensing record form to provide to their Pharmacist requesting anticoagulant dispensing information required for the study. The printout will be collected by the patient or a study representative with permission from the patient.

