(ACE) Measure, a 12 question survey validated to measure patient engagement, and 7) Ten-Item Personality Inventory (TIPI), a ten question survey used to assess patient personality. The first six survey instruments will be incorporated into a baseline and follow-up patient survey to be built out in Survey Monkey®, an on-line tool to design, collect and analyze surveys and responses. The TIPI survey will be used only at the 6-month study follow-up visit. Survey Monkey enables covered entities to collect protected health information (PHI) in online surveys in a way that permits compliance with the Health Insurance Portability and Accountability Act of 1996 (HIPAA). SSL (Secure Sockets Layer), a protocol developed for transmitted private documents or information via the internet, creates a secure connection between a client and a server, encrypting sensitive information being transmitted through the web page. After consenting participants, we will ask them to complete demographic information and survey (Table 2).

Patient surveys will be comprised of questions aimed at assessing patient engagement, health literacy, and medication adherence. Patient engagement will be assessed using the validated survey instruments, the Patient Activation Measure (PAM) and the Altarum Consumer Engagement (ACE) Measure, number of logins to MyChart and secure messaging activity with provider/health coach. We will also evaluate health literacy using questions aimed at patient understanding of anticoagulant use in AF. Medication adherence will be measured using the MAS validated survey instrument developed by Morisky and patient pharmacy refill records. In an attempt to make the medication adherence data more robust, we will extract refill record data from electronic prescribing software (Surescripts) on study patients. In addition, all patients will use smart pill bottles to dispense their anticoagulation medication. These bottles will track medication adherence by the opening of the bottle cap, and will record data accordingly. The bottles will not be set up to alert patients or deliver any intervention for medication adherence.

In order to determine the exact tailored health messaging patients will receive, study staff will identify the following information in patients' electronic health records:

1. Duration of time since AF diagnosis (Approximate days, months, and/or years)
2. Current oral anticoagulant prescribed

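### Does the Phase 2 statement that the smart bottles deliver no adherence intervention contradict their use as a trigger for MyChart messages?

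*Protocol*

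**What the plan says.** The Protocol Synopsis (Purpose) states "One trigger for health education messaging will be failure to take, fill, or refill anticoagulant medication prescription". The Phase 1 section d.) Intervention Build repeats this almost word for word, "One trigger for health education messaging used in the intervention will be failure to take, fill, or refill anticoagulant medication prescription", and describes the bottle as a device that "sends notification in real time when participants open or fail to open their pill bottle". Table 1 lists, under the Phase 1 build, "build trigger from Surescripts data feed and AdhereTech smart pill bottle; implement educational messaging in PHR".

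Phase 2 takes that build into the trial. Its introduction says "we will conduct a 6-month trial of the intervention designed and built in Phase 1 of the study", and the list for the experimental group says "patients in this group will have the MyChart intervention designed and built in Phase 1 of this study".

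Phase 2, c) Quantitative Data Collection and Analysis, gives all patients a smart bottle that records cap openings, and adds "The bottles will not be set up to alert patients or deliver any intervention for medication adherence". It then says "In order to determine the exact tailored health messaging patients will receive, study staff will identify the following information", followed by five chart items: time since AF diagnosis, current anticoagulant, time on it, any earlier switch, and the previous drug. Phase 2, e) Intervention, describes the algorithm in the past tense as resting on four characteristics of the same kind. Neither list names a missed dose or a missed refill.

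**The concern.** The synopsis and the build section suggest messages that respond to lapses in adherence. The Phase 2 description, read alone, suggests education chosen from clinical history, with the bottles used only for measurement. These are different interventions, and a report of Aim 2 could credit its result to either one.

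Two further effects seem possible if the bottle trigger is active. The tool that measures adherence in both arms would also drive the intervention in one of them. And MyChart logins, which the protocol counts as a sign of engagement, could rise in the experimental arm because patients missed doses and were messaged about it.

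**Working it through.** The point is textual, so the passages are compared first and the one related figure is checked afterwards.

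**1. Who delivers the message?** The synopsis, the study hypothesis, the build section, the experimental-group list and e) Intervention all have the messages travel through MyChart or the personal health record. In the synopsis and the build section the bottle's part is to supply information. The disputed Phase 2 sentence has the bottles as its subject, and it follows directly on the statement that every patient uses one. A bottle that gives no alert and delivers nothing can still send data that lead to a MyChart message. The two statements are compatible on that reading, although the protocol never spells it out.

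**2. Do the Phase 2 lists exclude a trigger?** The five chart items and four algorithm inputs determine which messages a patient receives. A trigger determines when one is sent. Fixed content can coexist with event-driven timing, for the bottle as much as for the refill feed named in the same sentence. The lists fit an active trigger and an inactive one equally well.

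**3. Does Table 3 settle it?** Its 50 rows include the daily bottle report but no row for any message sent to a patient, not even for the tailored messages that are certainly sent. The absence of a row for triggered messages therefore says nothing about whether they exist.

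**4. What changes for the comparison?**

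| Element | Trigger active | Trigger inactive |
|---|---|---|
| Bottle in both arms | yes | yes |
| MyChart training in both arms | yes | yes |
| Tailored messages | experimental arm only | experimental arm only |
| Recording of openings and refills | same in both arms | same in both arms |
| Contrast estimated | messaging package against none | messaging package against none |

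**5. Sample size.** Inputs, from the sample-size note under Phase 2, i. Patient Selection: SD of the medication possession ratio 10%, difference 5%, two-sided 5% level, power 80%, dropout 20%.

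- Normal approximation: n = 2 × (1.960 + 0.842)² × 10² / 5² = 2 × 7.85 × 4 = 62.8, so 63 per group.
- Two-sample t-test: 63.8, so 64 per group, as stated. Power at 64 per group is 80.1% (80.7% by the normal approximation).
- Enrolment: 64 / (1 − 0.20) = 80 per group, 160 in total, as stated.

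None of these inputs depends on whether the trigger is active.

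**6. How many extra messages?** The documents give neither a message frequency nor a rate of missed openings. Any count would rest on invented inputs, so none is offered.

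**The case for a change.** The strongest case for a change is that the content of the experimental arm belongs in the protocol and should not be left to inference. The synopsis covers the whole study, states the trigger in the future tense, and is not marked as superseded. The build section allows for adjustments but records none. The Phase 2 sentence excludes any adherence intervention by the bottles, which is broad wording, and the section meant to describe the intervention never mentions the trigger. Staff and readers cannot tell from the text which version ran. That section also keeps patients who permanently stop their anticoagulant in the study, without saying whether their unopened bottles would lead to messages.

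Part of this stands. The Phase 2 Intervention section is silent where one sentence would have helped, and the wording about the bottles is loose. But silence together with an ambiguous verb is not a contradiction. The engagement point also carries less weight than it seems to: messages reach the experimental arm through MyChart under either reading, so a difference in logins already partly reflects the messages themselves. An active trigger would add to that effect but would not create it.

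**Conclusion.** No change to the plan follows. The passages leave open whether bottle and refill data prompt MyChart messages during the trial, but they can be read together without conflict: the bottle informs, MyChart delivers, and the device itself stays silent in both arms. The study team knows which version it built and can say so when it describes the intervention in the report.

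The effect on the stated figures is nil: 64 completing and 80 enrolled per group hold either way. The randomised contrast is tailored messaging against none on top of the same bottle and training, and it is sound under both readings. This conclusion assumes that one version ran throughout at this single site and that openings and refills were recorded alike in both arms, as the protocol describes. What remains is a caution in interpretation: the Aim 2 result belongs to the messaging package as actually delivered, and login counts should not be read as a pure measure of engagement.
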